10.2.1 Instructions for Male Patients

Male patients must agree to use an effective barrier method of contraception during the study and for a minimum of 18 weeks after the last dose of study drug if sexually active with a WOCBP.

10.3 Scheduled Activities and Trial Visits

10.3.1 Screening Period

The Screening Period will start with the Screening visit and continue until randomisation. The ICF/IAF must be signed before any trial-related procedures are performed.

Before signature of the ICF/IAF, Investigators will evaluate eligibility of patients for entry in the trial by comparing past and current medical status, as documented in the patient's medical records, to the trial's inclusion/exclusion criteria.

Eligible patients will receive a detailed description of all activities and requirements before signing the ICF/IAF to ensure their understanding and compliance with sample collection, clinical examination, and eDiary completion requirements

Patients who require a washout period from prohibited concomitant treatments should be seen and sign the ICF/IAF before the Screening visit to ensure the necessary washout period is met as required based on the type of background therapy taken. No trial assessments will be performed on that date and the Screening visit will be scheduled according to the washout length required for the specific medication stopped.

The Screening visit and assessments will be performed in accordance with the schedule detailed in [Table 1](#).

10.3.2 Treatment Period

Treatment period visits and assessments will be performed in accordance with the SoA detailed in [Table 1](#). See [Sections 10.4](#) and [Section 10.5](#) for details on the efficacy and safety assessments, respectively.

The trial visits cannot be repeated or skipped but may be postponed (if not started yet) within the time windows allowed in this protocol, in case of:

- technical problems with the equipment necessary for the visit
- any AEs that impede the conduct of the visit
- the intake of any prohibited medication, to reach the washout length required in the specific prohibited medication section of the protocol, as long as the delay fits the protocol-allowed time window.

10.3.3 End-of-Treatment

End-of-treatment visit and assessments will be performed in accordance with the SoA detailed in [Table 1](#), after the last study drug administration (for completed patients) or premature discontinuation visit (when applicable).

10.3.4 Follow-up Period

A follow-up visit and assessments will be performed in accordance with the SoA detailed in [Table 1](#), after the last study drug administration (for completed patients) or premature discontinuation visit (when applicable).

10.3.5 Unscheduled and Repeated Tests

Unscheduled Tests

As deemed necessary by the Investigator, additional safety test(s) can be performed at any time during the trial to follow-up with the progress of any clinically relevant abnormal finding, investigate any potential new AE, etc. These additional tests outside of the initial schedule of the trial will be considered "unscheduled tests" and will not be associated with any trial visit.

Repeated Tests

Any safety test may be repeated at the Investigator's discretion under either of the following situations:

- When there is any kind of problem with the first test (ie, blood sample haemolysed, presence of artefacts). The Investigator should repeat the individual test as soon as possible.
- At the Screening visit, any individual test(s) may be reasonably repeated before randomisation to confirm the eligibility criteria (eg, laboratory sample when there is any clinically significant abnormality).

The new test will be considered a "re-test" and will be identified with the same visit ID as the first attempt.

10.4 Efficacy Assessments

Each patient's AD will be assessed as specified in the SoA ([Table 1](#)). Whenever possible, the same assessor should perform all assessments on a given patient during the course of the study. The Sponsor or delegate will administer training on the required efficacy assessments, and details on the specific instruments and training given will be recorded in the study training materials. If a parent or caregiver helps an adolescent patient complete an assessment or questionnaire, they must not influence or question the response given by the adolescent patient with AD. This requirement should be communicated to the parent or caregiver during training on eDiary completion.

10.4.1 Eczema Area and Severity Index Score

The EASI is used to assess the severity and extent of AD; it is a composite index with scores ranging from 0 to 72, with higher values indicating more severe and or extensive disease.⁴⁸ The severity of erythema, induration/papulation, excoriation, and lichenification will be assessed

by the Investigator or trained designee on a scale of 0 (absent) to 3 (severe) for each of the 4 body areas: head/neck, trunk, upper limbs, and lower limbs, with half points allowed. In addition, the extent of AD involvement in each of the 4 body areas will be assessed as a percentage by body area of head/neck, trunk, upper limbs, and lower limbs, and converted to a score of 0 to 6. Assessors must be trained and certified by the Sponsor or delegate before conducting this assessment.

10.4.2 Investigator Global Assessment

The IGA is an instrument used to globally rate the severity of the patient's AD. It is based on a 5-point scale ranging from 0 (clear) to 4 (severe), and a score is selected using descriptors that best describe the overall appearance of the lesions at a given time point. Assessors must be trained and certified by the Sponsor or delegate before conducting this assessment.

Table 7. Investigator Global Assessment

Score	Grade	Definition
0	Clear	Minor, residual discolouration; no erythema or induration/papulation; no oozing/crusting; no oedema.
1	Almost clear	Trace, faint-pink erythema with barely perceptible induration/papulation and no oozing/crusting; no oedema.
2	Mild	Faint-pink erythema with papulation and oedema perceptible upon palpation and no oozing/crusting; minimal induration.
3	Moderate	Pink-red erythema with definite oedema of skin papules and plaques; there may be some oozing/crusting; palpable induration.
4	Severe	Deep/bright red erythema with significant swelling and obvious raised borders of papules and plaques with oozing/crusting; significant induration.

10.4.3 Body Surface Area

The BSA assessment estimates the extent of disease or skin involvement with respect to AD and is expressed as a percentage of total body surface. BSA will be determined by the Investigator or designee using the patient palm = 1% BSA rule. Assessors must be trained and certified by the Sponsor or delegate before conducting this assessment.

10.4.4 Scoring Atopic Dermatitis

The SCORAD is a validated clinical tool for assessing the extent and intensity of AD.³⁸ There are 3 components to the assessment:

- The AD surface involvement is assessed as the proportion of involved surface area segment by segment by applying the rule of 9s (eg, 50% of the right leg = 4.5) and reported as the sum of all areas, with a score ranging from 0 to 100.
- The intensity part of the SCORAD consists of 6 items: erythema, oedema, oozing/crusting, excoriation, lichenification, and dryness. Each item is graded as follows: none (0), mild (1), moderate (2), or severe (3) (for a maximum of 18 total points).

- Subjective assessment of itch and of sleeplessness is recorded for each symptom using a visual analog scale (VAS), where 0 is no itch (or sleeplessness) and 10 is the worst imaginable itch (or sleeplessness), for a maximum possible score of 20.

The SCORAD Index formula is: $A/5 + 7B/2 + C$. In this formula “A” is defined as the extent (0-100), “B” is defined as the intensity (0-18), and “C” is defined as the subjective symptoms (0-20). The maximum score of the SCORAD Index is 103.

Assessments will be reported by the clinician and the patient (VAS only), as outlined in the SoA (Table 1).

Assessors must be trained and certified by the Sponsor or delegate before conducting this assessment.

10.4.5 Pruritus Numerical Rating Scale

The Pruritus NRS is an 11-point scale used by patients to rate their worst itch severity over the past 24 hours, with 0 indicating “No itch,” and 10 indicating “Worst itch imaginable.”⁴⁹ Assessments will be recorded by the patient using an eDiary, as outlined in the SoA (Table 1).

The Baseline Pruritus NRS will be determined based on the average of daily Pruritus NRS scores during the 7 days immediately before Baseline. A minimum of 4 daily scores out of the 7 days immediately before Baseline is required for this calculation.

10.4.6 Sleep-Loss Scale

Sleep loss will be assessed by all patients using a PRO instrument. Patients (and if applicable, with help of parents/caregiver if required) will rate their sleep on a 5-point Likert scale (with scores ranging from 0 [not at all] to 4 [unable to sleep at all]). Assessments will be recorded by the patient using an eDiary, as outlined in the SoA (Table 1).

10.4.7 Skin Pain NRS

The Skin Pain NRS is a patient-administered, validated, 11-point horizontal scale anchored at 0 and 10, with 0 representing “no pain” and 10 representing “worst pain imaginable.” Overall severity of a patient’s skin pain is indicated by selecting the number that best describes the worst level of skin pain in the past 24 hours.⁵⁰ Assessments will be recorded by the patient using an eDiary, as outlined in the SoA (Table 1).

The Baseline Skin Pain NRS will be determined based on the average daily Skin Pain NRS scores during the 7 days before Baseline. A minimum of 4 daily scores out of the 7 days before Baseline is required for this calculation.

10.4.8 Patient-Oriented Eczema Measure

The POEM is a 7-item, validated questionnaire completed by the patient (and, if applicable, with help of parents/caregiver if required) to assess disease symptoms.⁵¹ Patients are asked to respond to questions on skin dryness, itching, flaking, cracking, sleep loss, bleeding, and weeping. All answers carry equal weight, with a total possible score ranging from 0 to 28 (answers scored as: No days = 0; 1-2 days = 1; 3-4 days = 2; 5-6 days = 3; every day = 4). A high score is indicative of a poor QoL. POEM responses will be captured using an eDiary, as outlined in the SoA (Table 1).

10.4.9 Dermatology Life Quality Index

The DLQI is a 10-item validated questionnaire completed by the patient or caregiver used to assess the impact of skin disease on the patient's QoL during the previous week.⁵² The 10 questions cover the following topics: symptoms, embarrassment, shopping and home care, clothes, social and leisure, sport, work or study, close relationships, sex, and treatment. Each question is scored from 0 to 3 ("not at all," "a little," "a lot," and "very much"), giving a total score ranging from 0 to 30. A high score is indicative of a poor QoL. DLQI responses will be captured as outlined in the SoA (Table 1).

Adolescents younger than age of 16 years will use the CDLQI, which is based on a set of 10 questions different from those of the DLQI.⁵³

10.4.10 Dermatology Life Quality Index-Relevant

The DLQI-R is a recently developed scoring tool that adjusts the total score of the DLQI questionnaire for the number of not relevant responses indicated by a patient.⁵⁴⁻⁵⁶

10.4.11 World Health Organisation - Five Well-Being Index

The WHO-5 assessment is a self-reported measure of current mental well-being covering 5 positively worded items, related to positive mood (good spirits, relaxation), vitality (being active and waking up fresh and rested), and general interests (being interested in things).⁴⁴ Each item is rated on 6-point Likert scale, ranging from 0 (at no time) to 5 (all of the time). The raw scores are transformed to a score ranging from 0 to 100, with lower scores indicating worse well-being. WHO-5 responses will be captured from the patient as outlined in the SoA (Table 1).

10.4.12 Recap of Atopic Eczema

The RECAP is a 7-item patient-reported instrument to capture eczema control, over the previous week.⁵⁷ Each item is scored on a 5-point Likert scale, ranging from 0 (very good) to 4 (very bad). A higher score indicates worse eczema control. RECAP responses will be captured from the patient as outlined in the SoA (Table 1).

10.4.13 Treatment Satisfaction Questionnaire for Medication-9 Items (TSQM-9)

The TSQM-9 is a 9-item measure that assesses the most common dimensions patients use to evaluate their medication (ie, global satisfaction, effectiveness, and convenience).⁴⁶ The results for each scale are presented from 0 to 100, where higher scores represent better satisfaction. TSQM-9 responses will be captured from the patient as outlined in the SoA (Table 1).

10.5 Safety and Tolerability Assessments

10.5.1 Adverse Events

See [Section 10.6](#) for AE definitions and reporting requirements.

10.5.2 Medical History, Physical Examinations, and Vital Signs

10.5.2.1 Medical History

A detailed medical history will be obtained by the Investigator or qualified designee at the Screening visit and recorded in the eCRF. The medical history will include immunisation records (for adolescent patients) and clinically relevant medical conditions or surgeries, including more specific information on a history of conjunctivitis and herpes infection/zoster. Information on the patient's AD (years since AD was diagnosed, anatomical areas affected by AD) and comorbidities (past history of asthma, allergic rhinitis/hay fever, conjunctivitis, food allergies, alopecia areata, prurigo nodularis, chronic hand eczema, herpes zoster [shingles], chickenpox [varicella-zoster], herpes simplex [eczema herpeticum, labialis (oral), genital], and eosinophilic esophagitis) will be collected and include the date of onset, extent of involvement, and past treatments for AD (and main reason for discontinuation) as well as comorbidities.

Patient medical history should include information on clinically significant personal history, including identification of major cardiovascular risk factors, current and past smoking history, current alcohol use, and past history of infections, malignancies, and major cardiovascular conditions.

10.5.2.2 Physical Examinations

A complete physical examination will include, at a minimum, assessments of the cardiovascular, respiratory, gastrointestinal and neurological systems. Height and weight will also be measured and recorded to allow calculation of body mass index. For this, patients should be in light indoor clothes without shoes. Specific head and neck lesions will be assessed at Baseline, Week 16, Week 32 and Week 52.

10.5.2.3 Vital Signs

Measurement of vital signs will include systolic and diastolic blood pressure (mmHg), pulse, respiratory rate (breaths per minute), and body temperature (°C). Measurements of systolic and diastolic blood pressure will be carried out after at least 5 minutes of resting in the supine position and always on the same arm. If there is any suspicion of an unreliable measurement, blood pressure will be measured again. The value obtained from the repeated measurement will be considered as definitive and should be recorded in the eCRF.

Significant findings that are observed after the patient has signed the ICF/IAF and that meet the definition of an AE must also be recorded in the eCRF.

10.5.3 Laboratory Testing

Blood and urine will be collected from each patient as specified in the SoA ([Table 1](#)) or as clinically indicated. Routine laboratory assessments will be analysed at a designated central laboratory (see [Section 4.3](#)). Tests to be performed are detailed in [Table 8](#).

Table 8. Laboratory Testing Parameters

Assessment	Specific Tests
Haematology	Haematocrit, haemoglobin, erythrocytes (red blood cells count), mean corpuscular volume, Mean corpuscular haemoglobin, Mean corpuscular haemoglobin concentration, leucocytes (white blood cells count), differential blood count (absolute and percentage of neutrophils, lymphocytes, monocytes, eosinophils and basophils), thrombocytes (platelet count)
Coagulation	At Screening only: Prothrombin time, activated partial thromboplastin time, and International Normalised Ratio
Blood chemistry	Electrolytes : Sodium, potassium, chloride, calcium, inorganic phosphate Enzymes : alanine aminotransferase, aspartate aminotransferase, alkaline phosphatase, gamma-glutamyl transferase, and lactate dehydrogenase Substrates : Total cholesterol, triglycerides, urea, creatinine, total bilirubin, total protein, albumin, uric acid, and blood urea nitrogen
Serology	At Screening only: Hepatitis B surface antigen, Hepatitis B core antibody, Ig antibodies, anti-hepatitis C virus antibodies, and HIV I/II antibodies and antigen (serum)
Urinalysis	Dipstick measurements will be performed at the trial site* and will include: specific gravity, pH, blood, leucocytes, protein, glucose, bilirubin, urobilinogen, ketones and nitrates *If relevant abnormalities are detected (eg, > ++ positive result in dipstick), the urine sample will be sent to the central laboratory for analysis.
Pregnancy Testing	A serum beta-hCG test will be performed in all women of childbearing potential at Screening. All pre-menopausal women who are not sterile at Screening will also have a urine pregnancy test performed locally at all visits. Any woman with a confirmed positive pregnancy test during Screening is not eligible for randomisation. A positive urine pregnancy test during the treatment period of the trial requires a serum beta-hCG test to confirm the result.

Abbreviations: hCG = human chorionic gonadotropin; HIV = Human Immunodeficiency Virus; Ig = Immunoglobulin.

Blood and urine samples for laboratory testing will be collected in appropriate sampling tubes at scheduled time highlighted in the SoA ([Table 1](#)).

10.6 Adverse Events

The Investigator will closely monitor any AE and will adopt the necessary clinical measures to ensure the safety of the patient.

10.6.1 Definitions

Adverse Event

An AE is defined as any untoward medical occurrence in a clinical trial participant, regardless of the administration of the IMP and its causal relationship to it.

An AE can therefore be any unfavourable and unintended medical occurrence during the patient's participation in the trial, including deterioration of a pre-existing medical condition, an abnormal value in a laboratory assessment, or an abnormal finding in the physical examination.

AEs must be temporally associated with the patient's participation in the trial; ie, occur after the patient signs the ICF/IAF. At the time of the occurrence of an AE, the administration of the IMP does not need to have been initiated yet. If initiated, it does not necessarily need to have a positive causal relationship to the event.

Adverse Events of Special Interest

The following TEAEs are being designated as Adverse Events of Special Interest (AESI):

- conjunctivitis
- herpes infection or zoster

The Investigator must report any AESIs within 48 hours from the moment she/he first learns of it to the Sponsor **PPD** pharmacovigilance unit. Additional data will be collected for AESIs during the treatment and follow-up phases. A specific follow-up form for conjunctivitis will be provided to the site. Patient records will include any follow-up information regarding these AESIs.

Serious Adverse Event

An SAE is an AE, that falls into 1 or more of the following categories:

- results in death
- is life-threatening (ie, an event that, in the view of the Investigator, places the patient at immediate risk of death from the event as it occurred.) It does not mean that the event might hypothetically have caused death if it were more severe or had lasted longer
- requires in-patient hospitalisation or prolongs existing hospitalisation
- results in persistent or significant disability or incapacity
- is a congenital anomaly or birth defect
- is any other medically important event that may jeopardise the patient or may require intervention to prevent one of the other above outcomes

Medical and scientific judgment should be exercised in deciding whether or not other situations should be considered serious reactions, such as important medical events that might not be immediately life-threatening or do not result in death or hospitalisation, but may jeopardise the patient or may require intervention to prevent one of the other outcomes listed in the definition above, should also be considered serious. These are considered "other important Medical events."

Hospitalisation is defined as an overnight stay at the hospital or emergency room.

Prolongation of hospitalisation is defined as any extension of an in-patient hospitalisation beyond the stay anticipated/required in relation to the original reason for the initial admission, as determined by the Investigator or treating physician.

10.6.2 Reporting of Adverse Events

AEs either reported by the patient or observed by the Investigator must be recorded on the AE page of the eCRF and should be described in the following manner:

- The nature of the AE will be described in precise, standard medical terminology (ie, not necessarily the exact words used by the patient). If known, a specific diagnosis should be recorded instead of listing signs and symptoms (eg, allergic contact dermatitis).
- The duration of the AE will be described by the start date and end date.
- The intensity of the AE will be described in terms of mild, moderate or severe according to the Investigator's clinical judgment. And assign to 1 of the following categories:
 - **Mild:** Awareness of event, symptoms or signs, but easily tolerated (acceptable).
 - **Moderate:** Sufficient discomfort and interferes with usual activity (disturbing).
 - **Severe:** Incapacitating with inability to do normal daily living activities or significantly affects clinical status, and warrants intervention (unacceptable).
- The causal relationship of the event to the use of the IMP will be described as:
 - **Not related:** Event or laboratory test result abnormality, definitely not related to study drug, or as related to another drug, chemical, or underlying disease.
 - **Unlikely related:** Event or laboratory test result abnormality, with a time relationship to study drug administration that makes a relationship improbable; disease or other drugs, chemicals or underlying disease provide plausible explanations.
 - **Possibly related:** Event or laboratory test result abnormality with a reasonable time relationship to study drug administration; could also be explained by underlying disease or other drugs or chemicals; information on drug withdrawal may be lacking or unclear.
 - **Related:** Event or laboratory test result abnormality with a reasonable time relationship to study drug administration, unlikely to be attributed to underlying disease or other drugs or chemicals; response to withdrawal clinically reasonable (positive dechallenge).

Possibly related and related terms will be considered "related" for reporting purposes. If the events are assessed as unlikely related or not related to the suspect IMP, the event does not qualify for reporting purposes. In the absence of information on causality from the reporting Investigator, PPD will immediately contact the reporting Investigator to request a causality assessment. The case will be updated with the follow-up information and reported accordingly. If no causality is provided by the Investigator, the Sponsor assessment will be considered for submission purposes.

- The outcome of the event will be described as:
 - Recovered/resolved
 - Recovering/resolving
 - Recovered/resolved with sequelae
 - Not recovered/not resolved
 - Fatal
 - Unknown
- The action taken on the study drug will be captured as:

- Drug withdrawn
- Not applicable

AEs will be collected only once with its maximum severity, except when the AE started before first IMP administration, persisted after it and worsened in severity any time after first IMP administration. In this latter case, the AE will be collected with each respective severity. The AE term recorded must be exactly the same in the different time points where AE is reported in the eCRF.

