9.5 Treatment Compliance

Study drug compliance will be assessed by counting returned used or unused prefilled syringes. A patient will be considered compliant with the dosing regimen if the patient received $\geq 75\%$ of the expected number of injections while enrolled in the study. Deviation(s) from the prescribed dosage regimen should be recorded in the eCRF.

Patients will be instructed to return all used and unused TCS medication (tubes) to the study site for accountability purposes. Information on the areas where TCS was administered as well as the type of TCS will also be collected. The Investigator must keep an accurate record of the number of tubes received, dispensed/used, and returned by patients. The Sponsor or designee will provide forms to facilitate inventory control. All accountability forms and treatment logs must be retained in the Investigator's permanent study file, and these records must be available for inspection at any time by the Sponsor, its designees, or by regulatory agencies.

The dosing logs for each patient will be kept during the trial. The Clinical Research Associate (CRA)/Monitor will review treatment compliance during monitoring site visits.

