11.8.4 Analysis of Safety and Tolerability Endpoints

The analyses of safety and tolerability outcomes will be performed on the SAF. Safety outcomes include AEs, vital signs (including body temperature, respiratory rate, pulse, and systolic and diastolic blood pressure), physical examinations (including application site reactions), and clinical laboratory assessments (haematology, chemistry panel, urine testing, and urine pregnancy test for WOCBP).

Baseline will be defined as the latest value before IMP administration on Day 1 of the study. In case of missing predose values, the value at Screening will be regarded as the Baseline value. For the follow-up visit the comparisons will be performed against Screening values.

Safety variables:

- AEs will be summarised as an overall proportion of patients with at least one AE, proportion of patients with at least one SAE, proportion of patients with at least one severe AE, proportion of patients with at least one related AE, proportion of patients with at least one AE leading to treatment or study discontinuation. Each patient will contribute only once (eg, the first occurrence) to each of the rates, regardless of the number of occurrences (events) the subject experiences.
- Treatment-emergent AEs will be summarised and tabulated by System Organ Class and PT, by severity (mild, moderate, severe), by seriousness, by action taken with the study drug (continued, interrupted or discontinued), by outcome (Recovered/resolved, Recovering/resolving, Recovered/resolved with sequelae, Not recovered/not resolved, Fatal, unknown), by relationship to study product (not related, unlikely related, possibly related, and related), and for AEs of clinical interest.

[figure not shown]
- An AE will be considered a TEAE if it was not present before the first dose of study drug or was present before the first dose of study drug but increased in severity during the treatment period. Any event with a missing onset date will be included as a TEAE.
- Deaths and SAEs will be listed by subject.
- Clinical Laboratory Tests: Laboratory parameters will be summarised using descriptive statistics at Baseline and at each subsequent pre-defined time point by treatment group. In addition, shift tables (ie, low-normal-high at Baseline versus low-normal-high at follow-up in a 3-by-3 contingency table) will be provided to assess changes in laboratory values from Baseline to follow-up in each treatment group and overall.

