14.2 Patient Information and ICF/IAF

Patients will be informed by the Investigator in detail of the characteristics of the drug to be administered, the nature of the clinical investigation, the risks and the discomfort that can reasonably be expected as a result of their participation and the uses of the data, as described in the Patient Information Sheet.

The patients will be informed that they are free to withdraw their consent and suspend their participation in the trial at any time with no penalty or loss of benefits to which the patient is otherwise entitled. Administration of the drug may be interrupted, and a patient withdrawn from the trial at the discretion of the Investigator. The Investigator should justify his decision in the patient's eCRF.

Any patient considered by the Investigator to be suitable for inclusion must document his or her willingness to participate in the trial by giving his or her ICF/IAF in writing before starting any trial procedure by signing the ICF/IAF, which must be dated by the patient and the Investigator. At such time the patient must be given adequate time to understand the information provided and ask questions, if required. A copy of the signed ICF/IAF will be given to the patient. The original shall be kept on file by the Investigator. Any new relevant information that becomes available during the trial will be provided to the patient.

The Patient Information Sheet and ICF/IAF will include all elements required according to the applicable legislation. These documents or any modification will have been authorised by Almirall, S.A. and approved by the relevant IEC before use.

After the completion of the trial, lay summaries summarising main results from the trial will be made available for patients.

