10.5.3. Conjunctivitis

Conjunctivitis are events of special interest and will be identified using PTs nested within the categories of conjunctivitis and Keratitis as described in the Almirall Safety Topics of Interest:

The following tables and listings will be produced for the SAF:

- Summary of TEAE of conjunctivitis overall and by categories, and also describing severity, seriousness, outcome and action taken.
- Summary and/or listing of conjunctivitis and eye inflammation follow-up form
- A listing of patients with conjunctivitis

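### The protocol's list for action taken with study drug after an AE has no value for an interruption (or for treatment continued), so the planned safety output cannot attribute a skipped or delayed injection to an AE

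*Protocol*

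**What the plan says.** Protocol 10.6.2 requires that AEs "must be recorded on the AE page of the eCRF and should be described in the following manner", and then fixes the permitted values for intensity, causality, outcome and action taken. For the last, "The action taken on the study drug will be captured as" is followed by two items only: "Drug withdrawn" and "Not applicable".

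Protocol 11.8.4 plans to summarise treatment-emergent AEs "by action taken with the study drug (continued, interrupted or discontinued"). SAP 10.5.3 plans a conjunctivitis summary "also describing severity, seriousness, outcome and action taken", without naming the categories for action taken.

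SAP 10.1 lists the AE tables. None covers all treatment-emergent AEs by action taken; the nearest is AEs leading to discontinuation of study drug. Protocol 11.2 gives the SAP precedence where the two differ. SAP section 11, which lists changes from the protocol's analysis, does not mention this table.

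The protocol foresees interruption. Section 14.2 says: "Administration of the drug may be interrupted, and a patient withdrawn from the trial at the discretion of the Investigator". Section 10.3.2 allows a visit to be postponed within its window when an AE gets in the way. Section 9.5 says: "Deviation(s) from the prescribed dosage regimen should be recorded in the eCRF".

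**The concern.** A safety table can show only what its source field can hold. Here the field is specified with fewer values than the table needs, and the missing ones are those between no change and permanent withdrawal. Safety and tolerability, to Week 16 and to Week 68, are stated objectives. Whether an AE made a patient miss or delay an injection is a direct measure of tolerability, most relevant for conjunctivitis and herpes infection or zoster, the designated AEs of special interest. If the gap stays, a reader of the clinical study report may see no interruptions and take that as a finding, or may have no information on the question.

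**Working it through.** There is no figure to reproduce. The check sets the capture list beside the reporting categories, and then asks what each possible output would show.

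1. Mapping of Protocol 11.8.4 to Protocol 10.6.2 for action taken:

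| Reporting category (11.8.4) | Capture value (10.6.2) |
|---|---|
| Discontinued | Drug withdrawn |
| Interrupted | none |
| Continued | none |
| (no counterpart) | Not applicable |

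One of three reporting categories has a source, two have none, and one of the two capture values maps to no reporting category.

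2. Is this a general looseness between the two sections? No. For the same AE record, severity has 3 values in both places, relationship to study drug 4 in both, and outcome 6 in both. The mismatch is specific to action taken.

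3. Effect at record level. Take two conjunctivitis events: one led to a skipped injection, the other changed nothing. Neither is a withdrawal, so the only remaining value for both is the second one. They receive the same code, and no later programming of that field can separate them. This holds even if the second value is read as a stand-in for treatment continued.

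4. Effect at table level. There are two routes.
   - If the 11.8.4 categories are tabulated from the 10.6.2 list, the interrupted count is 0 in each arm by construction. SAP 13.2.5.2 keeps empty categories on display, so the 0 is printed. The continued row has the same gap.
   - If only the SAP 10.1 tables are produced, there is no such row for all AEs, and AE-related interruptions are not reported. The conjunctivitis summary in SAP 10.5.3 still needs the field.

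5. Can other planned data fill the gap?
   - Dosing deviations in the eCRF and per-patient dosing logs (Protocol 9.5) and patient-recorded study drug intakes (Protocol 12.1.3) record the missed injection. No link to an AE is described.
   - Syringe counts (Protocol 9.5, SAP 8.8) give compliance against a 75% threshold. From Baseline to Week 14 the schedule is 2 + 2 + 6 = 10 syringes (two at Baseline, two at Week 2, one at each of Weeks 4 to 14). A patient who misses two single injections has 8/10 = 80% and is compliant. An injection given late does not alter the count at all.
   - Exposure duration (SAP 8.7) is last dose date minus first dose date plus 1, and by its own note does not exclude missed doses. Percent of planned exposure falls when lebrikizumab is skipped, but carries no reason.

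None of these outputs attributes a skipped or delayed injection to an AE.

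**The case against.** The strongest reply is that the consequence is smaller than it looks. The SAP takes precedence and SAP 10.1 contains no all-AE table by action taken, so there may be no row to be falsely zero. The eCRF is not among the documents and may hold a fuller code list than Protocol 10.6.2. A break also separates the lead-in from its two items; nothing indicates that items are missing, but the page is easily checked. Missed doses are recorded in several places, and for conjunctivitis Protocol 10.6.1 promises additional data and a specific follow-up form, which SAP 10.5.3 will summarise or list. The listed safety endpoints include AEs leading to discontinuation of treatment, which the withdrawn value supports; AE-related interruption is not a listed endpoint.

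Much of this stands, and it limits the point in two ways. A reader might infer that interruptions will appear as zero in both arms whatever happens. The documents do not support that: it requires both that the eCRF follows the 10.6.2 list and that the 11.8.4 table is produced. A reader might also infer that skipped injections go unrecorded. They do not: deviations, logs, diary entries and syringe counts hold them. What is missing is the stated link to the AE.

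The reply does not remove the mismatch. The SAP's silence leaves a protocol-specified table dropped without a note, SAP 10.5.3 still depends on the field, and the contents of the conjunctivitis follow-up form are not given, so it cannot be assumed to capture dosing action.

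**Conclusion.** The inconsistency is real and within the protocol itself: two of the three planned categories for action taken have no capture value, and the listed values cannot identify an AE that led to a skipped or delayed injection. The result is either an artefactual zero or an unreported item, depending on which document's table list is followed.

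This rests on the eCRF following Protocol 10.6.2 as written. No number of affected patients can be given, because the documents contain no rate of AE-related missed injections. The effect is confined to descriptive safety reporting; the primary analysis and the sample size are unaffected. It is worth correcting because tolerability is a stated objective and the repair is cheap.

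**What to change.** In Protocol 10.6.2 and the eCRF code list, capture action taken as: dose not changed; drug interrupted (injection skipped or delayed); drug withdrawn; not applicable; unknown. Use the same categories in Protocol 11.8.4 and name them in SAP 10.5.3. For AEs already entered, match AE dates to the recorded dosing deviations and query the site where they coincide.

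In SAP 10.1, state whether the table of all treatment-emergent AEs by action taken is produced. If it is dropped, record that in SAP section 11. Deleting the unsupported categories from 11.8.4 would be a smaller repair and would make the documents agree, but it would leave AE-related interruptions unreported and the SAP 10.5.3 summary still dependent on an inadequate field.

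The cost is a code-list change, one protocol line, short SAP edits and some retrospective queries. The change concerns what is recorded and reported, not when treatment should be interrupted or stopped.
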